8.3. Lost to Follow-Up

A patient will be considered lost to follow-up if he or she repeatedly fails to return for scheduled visits and is unable to be contacted by the study site. Site personnel are expected to make diligent attempts to contact patients who fail to return for a scheduled visit or were otherwise unable to be followed up by the site.

9. Study Assessments and Procedures

Section 2 lists the Schedule of Activities, with the study procedures and their timing (including tolerance limits for timing).

Appendix 2 lists the laboratory tests that will be performed for this study.

Unless otherwise stated in the subsections below, all samples collected for specified laboratory tests will be destroyed within 60 days of receipt of confirmed test results. Certain samples may be retained for a longer period, if necessary, to comply with applicable laws, regulations, or laboratory certification standards.

9.1. Efficacy Assessments

9.1.1. Primary Efficacy Assessments

The primary efficacy endpoints to assess the proportion of patients maintaining efficacy achieved in the originator studies are as follows:

9.1.1.1. Static Physician's Global Assessment

The static Physician's Global Assessment (sPGA) is the physician's global assessment of the patient's psoriasis lesions at a given time point (EMA 2004). Plaques are assessed for induration, erythema, and scaling, and an overall rating of psoriasis severity is given using the anchors of clear (0), minimal (1), mild (2), moderate (3), severe (4), or very severe (5).

9.1.1.2. Psoriasis Area and Severity Index

The PASI is an accepted primary efficacy measurement for this phase of development of psoriasis treatments (EMA 2004). The PASI combines assessments of the extent of body-surface involvement in 4 anatomical regions (head, trunk, arms, and legs) and the severity of scaling, redness, and plaque induration/infiltration (thickness) in each region, yielding an overall score of 0 for no psoriasis to 72 for the most severe disease (Fredriksson and Pettersson 1978). The PASI has been the most frequently used endpoint and the measure of psoriasis severity in clinical trials (EMA 2004; Menter et al. 2008). A clinically meaningful response is a PASI 75, which represents at least a 75% decrease (improvement) from the baseline PASI score. Higher levels of clearance (PASI 90), as well as complete resolution of psoriasis (PASI 100), have become additional endpoints because of the increasing recognition of the association of higher clearance with greater health-related quality of life (HRQoL) (Puig 2015).

9.1.2. Secondary Efficacy Assessments

Secondary efficacy assessments will include the following:

9.1.2.1. Static Physician's Global Assessment

Both sPGA (0) and sPGA (0,1) will be assessed at various time points up to 4 years. For assessment description, see Section 9.1.1.1.

9.1.2.2. Psoriasis Area and Severity Index

PASI 75, PASI 90, and PASI 100 will be assessed at various time points up to 4 years. PASI 75, 90, and 100 are the percentage improvements in PASI (75%, 90%, and 100%, respectively). For assessment description, see Section 9.1.1.2.

9.1.2.3. Body Surface Area

Percent body surface area (BSA) will be evaluated as the percent involvement of psoriasis on each patient's BSA on a continuous scale from 0% (no involvement) to 100% (full involvement), where 1% corresponds to the size of the patient's hand (including the palm, fingers, and thumb) (National Psoriasis Foundation 2016).

9.1.2.4. Nail Psoriasis Severity Index

The Nail Psoriasis Severity Index (NAPSI) is used to evaluate the severity of fingernail bed psoriasis and fingernail matrix psoriasis by area of involvement in the fingernail unit. In this study, only fingernail involvement will be assessed. The fingernail is divided with imaginary horizontal and longitudinal lines into quadrants. Each fingernail is given a score for fingernail bed psoriasis (0 to 4) and fingernail matrix psoriasis (0 to 4) depending on the presence (score of 1) or absence (score of 0) of any of the features of fingernail bed and fingernail matrix psoriasis in each quadrant. The NAPSI score of a fingernail is the sum of scores in fingernail bed and fingernail matrix from each quadrant (maximum of 8). Each fingernail is evaluated, and the sum of all the fingernails is the total NAPSI score (range, 0 to 80).

9.1.2.5. Psoriasis Scalp Severity Index

The Psoriasis Scalp Severity Index (PSSI) measures the affected scalp area and the severity of clinical symptoms. The PSSI is a composite score derived from the sum of scores for erythema, induration, and desquamation multiplied by a score for the extent of scalp area involved (range, 0 to 72). Higher scores indicate worse severity (Thaçi et al. 2015).

9.1.2.6. Palmoplantar Psoriasis Severity Index

The Palmoplantar Psoriasis Severity Index (PPASI) is a composite score derived from the sum of scores for erythema, induration, and desquamation multiplied by a score for the extent of palm and sole area involvement (range, 0 to 72).

9.1.2.7. Health Outcomes Assessments

The following patient-reported questionnaires will be administered according to the Schedule of Activities (Section 2) in countries where the questionnaires have been translated into the native language of the region and linguistically validated. These assessments should be completed before administration of investigational product; before the patient's clinical examination; before the patient receives any tests or results; and before the patient's health, health data, or emotions are discussed.

9.1.2.7.1. Dermatology Life Quality Index

The Dermatology Life Quality Index (DLQI) is a validated, dermatology-specific, patient-reported measure that evaluates a patient's HRQoL. This questionnaire has 10 items that are grouped into 6 domains, namely symptoms and feelings, daily activities, leisure, work and school, personal relationships, and treatment. The recall period of this scale is over the "last week" Response categories include "not at all," "a little," "a lot," and "very much," with corresponding scores of 0, 1, 2, and 3, respectively, and unanswered ("not relevant") responses scored as "0." The total score ranges from 0 to 30 (less to more impairment) (Finlay and Khan 1994; Basra et al. 2008). A DLQI total score of 0 to 1 is considered as having no effect on a patient's HRQoL, and a 5-point change from baseline is considered as the minimal clinically important difference threshold (Khilji et al. 2002; Hongbo et al. 2005).

9.1.2.7.2. Psoriasis Symptoms Scale

The Psoriasis Symptoms Scale (PSS) is a patient-administered assessment of 4 symptoms (itch, pain, stinging, and burning); 3 signs (redness, scaling, and cracking); and 1 item on discomfort related to symptoms/signs. Respondents are asked to answer the questions based on their psoriasis symptoms.

The overall severity for each individual symptom/sign from the patient's psoriasis is indicated by selecting the number from a numeric rating scale from 0 to 10 that best describes the worst level of each symptom/sign in the past 24 hours, where 0=no symptom/sign and 10=worst imaginable symptom/sign.

The symptom severity scores, ranging from 0 to 10, are the values of the selected numbers indicated by the patient on the instrument's horizontal scale. Each of the 8 individual items will receive a score of 0 to 10 and will be reported as item scores for itch, pain, stinging, burning, redness, scaling, cracking, and discomfort. In addition, a symptoms score ranging from 0 (no symptoms) to 40 (worst imaginable symptoms), and a signs score of 0 (no signs) to 30 (worst imaginable signs) will be reported.

9.1.2.7.3. 16-Item Quick Inventory of Depressive Symptomatology-Self Report

The QIDS-SR16 is a self-administered, 16-item instrument intended to assess the existence and severity of symptoms of depression as listed in the American Psychiatric Association's Diagnostic and Statistical Manual of Mental Disorders, 5th Edition (DSM-V) (American Psychiatric Association 2013). A patient is asked to consider each statement as it relates to the way they have felt for the past 7 days. There is a 4-point scale for each item ranging from 0 to 3. The 16 items corresponding to 9 depression domains are summed to give a single score ranging from 0 to 27, with higher scores denoting greater symptom severity. The domains assessed by the instrument include: (1) sad mood, (2) concentration, (3) self-criticism, (4) suicidal ideation, (5) interest, (6) energy/fatigue, (7) sleep disturbance (initial, middle, and late insomnia or hypersomnia), (8) decrease/increase in appetite/weight, and (9) psychomotor agitation/retardation.

This instrument will also be used for AE monitoring (see Section [9.2.2](#)).

9.1.3. Appropriateness of Assessments

The clinical safety parameters in this study are standard elements of clinical health assessment and Phase 3 drug development. The disease activity and health outcome measurements are used both in clinical practice and psoriasis clinical trials. Psoriasis is associated with numerous skin-based symptoms and HRQoL impairment, which justifies the use of the psoriasis symptom severity as well as dermatologic and generic HRQoL assessments used in this study (EMA 2004; Kimball et al. 2005).

9.2. Adverse Events

Investigators are responsible for monitoring the safety of patients who have entered this study and for alerting Lilly or its designee of any event that seems unusual, even if this event may be considered an unanticipated benefit to the patient.

The investigator is responsible for the appropriate medical care of patients during the study.

Investigators must document their review of each laboratory safety report.

The investigator remains responsible for following, through an appropriate health care option, AEs that are serious or otherwise medically important, considered related to the investigational product or the study, or that caused them to discontinue the investigational product before completing the study. The patient should be followed until the event resolves, stabilizes with appropriate diagnostic evaluation, or is reasonably explained. The frequency of follow-up evaluations of the AE is left to the discretion of the investigator.

Lack of drug effect is not an AE in clinical studies, because the purpose of the clinical study is to establish treatment effect.

After the informed consent form (ICF) is signed, study site personnel will record via eCRF the occurrence and nature of each patient's preexisting conditions, including clinically significant signs and symptoms of the disease under treatment in the study. In addition, site personnel will record any change in the condition(s) and any new conditions as AEs. Investigators should record their assessment of the potential relatedness of each AE to protocol procedure investigational product, via eCRF.

The investigator will interpret and document whether or not an AE has a reasonable possibility of being related to study treatment, study device, or a study procedure, taking into account the disease, concomitant treatment or pathologies.

A "reasonable possibility" means that there is a cause and effect relationship between the investigational product, study device and/or study procedure and the AE.

The investigator answers yes/no when making this assessment.

Planned surgeries and nonsurgical interventions should not be reported as AEs unless the underlying medical condition has worsened during the course of the study.

If a patient's investigational product is discontinued as a result of an AE, study site personnel must report this to Lilly or its designee via eCRF, clarifying if possible, the circumstances leading to any dosage modifications, or discontinuations of treatment.

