9.2.1.1. Suspected Unexpected Serious Adverse Reactions

Suspected unexpected serious adverse reactions (SUSARs) are serious events that are not listed in the IB and that the investigator identifies as related to investigational product or procedure. United States 21 CFR 312.32 and European Union Clinical Trial Directive 2001/20/EC and the associated detailed guidances or national regulatory requirements in participating countries require the reporting of SUSARs. Lilly has procedures that will be followed for the identification, recording and expedited reporting of SUSARs that are consistent with global regulations and the associated detailed guidances.

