10.3.4. Safety Analyses

Safety assessments will include AEs, laboratory analytes, vital signs, ECGs, and C-SSRS. Safety data assessments will be summarized for the cohorts described in Section [10.3.1](#)

Adverse events will be coded according to the *Medical Dictionary for Regulatory Activities* and summarized by system organ class, preferred term, severity, and relationship to investigational product. A treatment-emergent adverse event (TEAE) is defined as an event that first occurred or worsened in severity after baseline. For each event classification term, the number of patients experiencing a TEAE with that classification term will be tabulated.

Treatment-related TEAEs are defined as events that are indicated by the investigator on the eCRF to be related to study treatment. If a patient reports the occurrence of a particular event more than once, the most severe of those events will be included in the summary table of TEAEs. For events that are gender specific, the denominator and computation of the percentage will only include patients from the given gender.

Adverse events of special interest are defined in Section [9.2.3](#), and the plan for analyzing AESIs will be described in the Program Safety Analysis Plan and SAP.

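### Protocol 9.2 defines a reasonable possibility of relatedness as an actual cause-and-effect relationship, so events could be under-classified as related to treatment

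*Protocol*

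**What the plan says.** Protocol 9.2 describes the relatedness call in three ways.

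- The recording instruction: "Investigators should record their assessment of the potential relatedness of each AE".
- The question: "The investigator will interpret and document whether or not an AE has a reasonable possibility of being related to study treatment". The investigator is to weigh the disease and other treatments or conditions, and the answer is binary: "The investigator answers yes/no when making this assessment".
- The definition of the key phrase: a reasonable possibility "means that there is a cause and effect relationship between the investigational product, study device and/or study procedure and the AE".

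The answer is used elsewhere in the protocol. Section 9.2.1.1 defines SUSARs as serious events not listed in the Investigator's Brochure "that the investigator identifies as related to investigational product or procedure". Section 10.3.4 plans AE summaries by relationship to investigational product and states: "Treatment-related TEAEs are defined as events that are indicated by the investigator on the eCRF to be related to study treatment". Section 9.2.1 makes two reporting duties conditional on the investigator thinking a relationship reasonably possible: SAEs after consent but before the first dose (relation to study procedure only), and SAEs that come to the investigator's notice after the patient has left the study.

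**The concern.** The question sets a threshold of suspicion, while the definition, read as written, sets one of established causation. There is no intermediate category such as possible or probable to hold an uncertain case. An investigator who thinks the drug may have contributed, but cannot say that it did, gets one answer from the question and the opposite answer from the definition.

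The consistency and direction of the relatedness classification are at stake, over up to 208 weeks of dosing in an expected 1600 to 2000 patients. Every patient receives mirikizumab, so there is no concurrent untreated group to supply a background event rate. The investigator's causality judgement therefore carries more interpretive weight than it would in a placebo-controlled trial.

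**Working it through.** No arithmetic applies: the documents state no related-event rate, SUSAR rate or other figure that could be reproduced. The check compares the wordings and then follows the answer to each place that uses it.

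**Step 1: what each wording implies for the three states of belief an investigator can hold.**

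| Investigator's belief | Answer by the question and by potential relatedness | Answer by the definition, read literally |
|---|---|---|
| No reason to suspect a link | No | No |
| Link plausible but not established | Yes | No |
| Link established | Yes | Yes |

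Only the middle row differs, and it differs in one direction: the literal definition can move events from related to unrelated, never the reverse.

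**Step 2: whether other text corrects the definition.** The sentence stands in the current Section 9.2 and is not among the sections revised by amendment (a). Section 9.2.1 uses an adverbial form of the same phrase without defining it again, and Section 9.2.1.1 simply refers to events identified as related. Nothing restores the lower threshold explicitly.

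**Step 3: what depends on the answer.**

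- *Treatment-related TEAEs (10.3.4):* defined by the investigator's eCRF entry, so directly affected.
- *SUSARs (9.2.1.1):* defined by the investigator's call, so affected at that step.
- *Follow-up of AEs (9.2):* relatedness is one trigger. Serious or medically important events, and those leading to discontinuation of the product, are followed in any case.
- *SAEs before the first dose (9.2.1):* the report to the sponsor depends on relatedness to a study procedure. The event is still recorded in the eCRF as an AE.
- *SAEs after the patient has left the study (9.2.1):* notification depends on relatedness, so such an event could go unreported.

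**Step 4: what does not depend on the answer.** Section 9.2.1 has every AE after consent recorded in the eCRF, and any SAE after dosing begins notified to the sponsor within 24 hours. Neither rule mentions causality. SAP 6.12 lists, for this study alone, listings and cohort summaries of SAEs and of AEs leading to permanent discontinuation, with no split by relatedness. The registry outputs in SAP 6.17 are organised by seriousness and preferred term.

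**The case against.** The strongest reply is that the sentence describes the kind of link meant, causal rather than merely temporal, and was never intended to demand proof. Appendix 1 supports this: it defines an AE as temporally associated with product use, related or not. On that reading, an investigator would answer the question actually put and say yes to a plausible link. This stands as far as it shows that the section is ambiguous rather than uniformly strict. It does not remove the conflict, because the sentence contains no word of possibility and some sites may take it at face value.

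A reader might infer that investigators following the protocol would under-report adverse events. The documents do not support that. AEs and post-dose SAEs reach the sponsor whatever the causality answer, so the general risk is misclassification. The two routes where reporting does depend on relatedness are narrow. For most patients Visit 1 coincides with the last originator visit, and after discharge the investigator has no duty to seek events actively.

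A reader might also infer that the investigator's answer is the sole determinant of SUSAR identification. Section 9.2.1.1 adds that "Lilly has procedures that will be followed for the identification, recording and expedited reporting of SUSARs", and Sections 9.4.6 and 10.3.8 provide for periodic sponsor review of aggregate safety data and for an external DMC. These are real safeguards. The causality standard in the sponsor's procedures is not stated, however, so they cannot be assumed to reverse an investigator's no.

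It is also fair that the effect on this study's planned tables is limited, given SAP 6.12. Protocol 10.3.4 nevertheless still commits to summaries by relationship, and SAP 6.12 sends the safety data on to integrated assessments.

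**Conclusion.** The definition in Protocol 9.2 is wrong as written: it is stricter than the phrase it defines and conflicts with potential relatedness in the same section. Applied literally, it could under-classify relatedness. This feeds the treatment-related TEAE category and the investigator step of the SUSAR definition. Suppression of reporting itself is confined to SAEs before the first dose and SAEs learned of after the patient has left the study.

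The direction is clear, towards fewer related events, but the size cannot be derived. It would depend on the share of events where investigators suspect but cannot affirm causation, and on how many of them follow the definition rather than the question; the documents give neither. The conclusion assumes only that some investigators apply the sentence as it reads.

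The point is worth correcting because it bears on safety classification and the remedy is simple. It does not call into question the capture of AEs or of post-dose SAEs.

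**What to change.** Reword the one sentence in Protocol 9.2 so that the definition matches the question. For example: a reasonable possibility means that there are facts or arguments to suggest that the investigational product, study device or study procedure may have caused the AE. Check that any eCRF completion guidance uses the same wording; that guidance is not among the documents, so its present content is unknown.

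The cost is one sentence in the next amendment or in a clarification letter. No treatment, visit, endpoint or analysis changes. The count of events classed as related may rise slightly. If the change is made while the study is running, the date should be recorded so that relatedness calls before and after it can be told apart.

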9.2.1. Serious Adverse Events

An SAE is any AE from this study that results in any of the following outcomes:

- Death
- Initial or prolonged inpatient hospitalization
- A life-threatening experience (that is, immediate risk of dying)
- Persistent or significant disability/incapacity
- Congenital anomaly/birth defect
- Important medical events that may not be immediately life-threatening or result in death or hospitalization but may jeopardize the patient or may require intervention to prevent one of the other outcomes listed in the definition above. Examples of such medical events include allergic bronchospasm requiring intensive treatment in an emergency room or at home, blood dyscrasias or convulsions that do not result in inpatient hospitalization, or the development of drug dependency or drug abuse.
- When a condition related to the prefilled syringes necessitates medical or surgical intervention to preclude either permanent impairment of a body function or permanent damage to a body structure, the serious outcome of "required intervention" will be assigned.

All AEs occurring after signing the ICF are recorded in the eCRF and assessed for serious criteria. The SAE reporting to the Sponsor begins after the patient has signed the ICF and has received the investigational product. However, if an SAE occurs after signing the ICF, but prior to receiving the investigational product, the SAE should be reported to the Sponsor as per SAE reporting requirements and timelines (see Section 9.2) if it is considered reasonably possibly related to study procedure.

Study site personnel must alert Lilly or its designee of any SAE within 24 hours of investigator's awareness of the event via a Sponsor-approved method. If alerts are issued via telephone, they are to be immediately followed with official notification on study-specific SAE forms. This 24-hour notification requirement refers to the initial SAE information and all follow-up SAE information. Patients with a serious hepatic AE should have additional data collected using the eCRF.

Pregnancy (during maternal or paternal exposure to investigational product) does not meet the definition of an AE. However, to fulfill regulatory requirements any pregnancy should be reported following the SAE process to collect data on the outcome for both mother and fetus.

Investigators are not obligated to actively seek AEs or SAEs in subjects once they have discontinued and/or completed the study (the patient disposition case report form has been completed). However, if the investigator learns of any SAE, including a death, at any time after a subject has been discharged from the study, and he/she considers the event reasonably possibly related to the study treatment or study participation, the investigator must promptly notify Lilly.

